7.3.4 Weight and Height

Participant height and weight will be assessed and recorded at enrollment. BMI will be calculated automatically and recorded.

7.3.5 Chest X-ray test

At the screening visit, a chest X-ray is performed on all subjects to determine suitability for the subject's safety.

7.3.6 12-Lead ECG

An ECG will be performed at screening for all subjects to determine eligibility. The ECG should include measurements of ventricular rate, PR, QRS, QT, QT_cF with assessment as to whether the ECG is normal or abnormal. Abnormal ECGs will be interpreted as clinically significant or not clinically significant. Dosing will be delayed in the event of a clinically significant abnormal pre-dose ECG until it has been reviewed by the PI, qualified PI designee, Medical Monitor or Sponsor consultant cardiologist and deemed safe to proceed. The ECG should be labeled as either "normal", "not clinically significant", avoiding abbreviations such as NCS, or "clinically significant, but stable to proceed" and kept with source documentation; alternatively case notes can reflect the ECG reading as source documentation. The method of QT_cF determination should also be recorded and will be collected as part of the Case Report Forms.

7.3.7 PCR or Antibody test (SARS-CoV-2)

At the screening visit, a point of care PCR or antibody test is performed on all subjects to determine serologic evidence of prior SARS-CoV-2 infection.

7.4 Assessment of injection site

The injection site will be assessed by study personnel at each visit. Participants are to be instructed to monitor the site for signs of inflammation, redness, swelling, or pain and report these issues at the next study visit. Site staff will discuss any symptoms and determine whether these constitute AEs and record as appropriate. The subject should be instructed to record the exact symptoms, the diameter of the redness (cm), the diameter of the edema (cm), the diameter of the bruise (cm), and the date of onset and disappearance.

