The Phase IIa portion of this study is designed as a randomized, double-blind, placebo-controlled study with only a single active study drug arm. Subjects will be randomized to receive either placebo or GLS-5310 vaccine in a 1:2 ratio. The primary and secondary goals of the Phase IIa study are the same as the Phase I study. Exploratory goals of the Phase IIa study are to determine the persistence of the immune response following vaccination with GLS-5310 and the extent of immune boosting for those who are enrolled and are seropositive at baseline. The study will be unblinded at the post-vaccination visit (study visit 4) at which time subjects will be informed of their treatment assignment. Subjects who were assigned to the placebo group will be offered to be vaccinated with GLS-5310. Subjects assigned to the placebo group who choose to be vaccinated with GLS-5310 will be followed for a year from 1st GLS-5310 vaccination (Table S4); subjects assigned to the placebo group but who decline vaccination with GLS-5310 will be followed for a year from study entry as per the original study protocol (Table S3).

Sub-studies

A sub-study will be included within the Phase IIa portion of CoV2-001 clinical trial.

Participants 66-85 years of age: 30 persons will be recruited into the study to examine whether immune responses in this age group are similar or different from those age 66-85 years of age.

The above subgroup will be randomized as part of the main study, and not separately randomized.

At randomization, the initial 5 subjects are set as the sentinel group to confirm the safety of the elderly group. When the sentinel group is vaccinated with the clinical trial drug, the vaccination is carried out at an interval of at least 24 hours between each subject. Five subjects aged 65 to 74 years will be enrolled as a sentinel group for the older age cohort. If there are no adverse drug reactions (ADRs) occurring within the 7 days after the first vaccination in the sentinel group, then enrollment into the older age cohort can proceed.

Study outcome will be based on the ITT analysis inclusive of all subgroups, however, subgroup analysis will be performed as above as an exploratory endpoint.

Sample size considerations:

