3.1 Interim Safety Monitoring

As part of the Phase I study, two interim safety reviews will be performed. A review of AE's and laboratory results will occur after all subjects in Study Arm 1a (0.6 mg) have received their 1st dose of vaccination and have completed the Week 1 safety visit. A formal Interim Analysis will be performed after study visit 4, four weeks after the 2nd vaccination to review AE's and binding antibody responses to select the vaccination regimen to be used for the Phase II study.

Subject diaries to be reviewed at the next visit after vaccination are distributed to the subjects, and symptoms of local and systemic reactions are collected and documented 7 days after vaccination.

As part of the Phase IIa study, an interim safety review will be performed after all participants have completed through the 4th study visit corresponding to the post-immunization visit after the primary vaccination series. Safety and immunogenicity will be determined and compared between groups as well as for the subgroup who are age 66 to 85.

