7. STUDY PROCEDURES AND TREATMENTS

7.1 Procedures by Visit (also see Tables S2 and S3)

7.1.1 Visit 1: Determine eligibility, obtain informed consent, enrollment, 1st vaccination

Prospective study participants will be assigned a unique participant identification number (PID#), and then interviewed to determine study eligibility.

Those who meet study criteria will complete an informed consent and be enrolled into the study to complete the following procedures:

- Review and record medical history (last 24 weeks)
- Review and record participant demographics
- Review and record prior and concomitant medications in past 24 weeks
- Perform and record physical examination and vital signs
- Record height and weight
- Collect blood for hematology and chemistry safety labs (baseline values)
- Collect blood for serological testing (Hepatitis B, Hepatitis A, HIV, Hepatitis C)
- Chest X-ray test
- 12-Lead ECG test
- PCR or Antibody screening test (SARS-CoV-2)
- Record most recent HgbA1c (diabetics only)
- Collect blood for immunology testing (serum and PBMCs baseline values)
- Collect urine for pregnancy testing (women of childbearing potential)
- Administer study drug (GLS-5310 or placebo depending on randomization results)
- Perform VAS score and record
- Distribution of subject diary after vaccination
- Check whether or not immediate adverse events (anaphylaxis-related) occur within 30 minutes after vaccination of the investigational drug (in case of the elderly over 75 years of age in Phase 2a, immediate adverse events are observed until at least 2 hours after vaccination of the investigational drug)

7.1.2 Visit 2: Safety follow-up.

Study procedures to be completed include:

- Review and record concomitant medications
- Perform targeted physical exam (relevant to participant system-specific complaints)
- Perform and record vital signs
- Review and record adverse events

- Review and record injection site reactions
- Review of subject diary
- Collect blood for hematology and chemistry

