7.3.3 Adverse effects

Adverse effects that will be queried at each study visit include those related to the underlying disease and treatment, those potentially related to study drug, and those potentially related to study drug administration. AEs should be graded according to the "Toxicity Grading Scale for Healthy Adult and Adolescent Volunteers Enrolled in Preventative Vaccine Clinical Trials" issued in September 2007 by the US FDA (Appendix A). Subjects record the response (local and systemic) after vaccination on the evening of each vaccination day and 7 days after each vaccination day in the subject diary (Appendix B).

Subjects record the response to the injection site using the measurement tool provided, and the investigator reviews the subject diary. The response results described are evaluated for clinical significance and recorded as appropriate in the CRF.

Subjects who develop Grade 1 or higher eosinophilia (eosinophil count of ≥ 650 cells/mm³) will be asked to return weekly for repeat CBC determinations until resolution of the eosinophilia.

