8.3.2 Stopping Rules

If any of the following situations occur, then further enrollment and Study Treatments will be halted immediately until a thorough investigation has been conducted by the Medical Monitor and PI and the IRB (if applicable):

- Any participant experiences a potentially life-threatening AE, Grade 4 AE or death assessed as related to Study Treatment;
- Any report of anaphylaxis of Grade 3 or greater assessed as related to Study Treatment.

Any SAE or death assessed as related to Study Treatment will lead to an immediate halt of study enrollment and Study Treatments, until the event has been investigated.

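### Section 7.4 has participants hold injection-site reactions until the next visit, with no exception for severe ones, and nothing is scheduled between the 30-minute check and Visit 2, which does not fit the 24-hour expedited reporting or the 24-hour sentinel interval

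*Protocol*

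**What the plan says.** **Participant to site.** Section 7.4 asks participants to "monitor the site for signs of inflammation, redness, swelling, or pain and report these issues at the next study visit". It names local signs only (inflammation, redness, swelling, pain) and sets no severity threshold for earlier contact. Section 7.3.3 is also tied to visits: "Adverse effects that will be queried at each study visit". The diary is filled in from the evening of vaccination through 7 days, but Section 3.1 defers its review: "Subject diaries to be reviewed at the next visit after vaccination are distributed to the subjects".

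**Immediate observation.** The Visit 1 list (Section 7.1.1) reads "Check whether or not immediate adverse events (anaphylaxis-related) occur within 30 minutes after vaccination of the investigational drug". For participants over 75, "immediate adverse events are observed until at least 2 hours after vaccination". The sentinels are aged 65 to 74, so the longer period does not apply to them. The next scheduled contact in Table S2 is Visit 2 at Week 1 ± 2 days.

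**Site to sponsor.** Section 8.3.1 lists Grade 3 or greater local or systemic symptoms, and related or possibly related allergic reactions, as events the site sends to the sponsor within 24 hours so that further dosing of that participant can be discussed. Under Section 8.3.2, when a halt trigger occurs, "further enrollment and Study Treatments will be halted immediately".

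**Sentinels.** The synopsis (Sub-studies) and Section 3 both say that "the vaccination is carried out at an interval of at least 24 hours between each subject". The synopsis opens the rest of the older cohort if the sentinels have no adverse drug reaction within 7 days of the first vaccination. Section 3 refers instead to reactions that meet the criteria for stopping vaccination, gives no period, and words the condition with a double negative.

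**The concern.** A 24-hour reporting rule works only if the site learns of the event. The one instruction in view on when a participant should report a site reaction points to the next visit, whatever the severity. The protocol foresees such events: its solicited-event table (Section 8.1.2.1.3) lists severe administration-site pain and, as a theoretical risk, severe localized reactions. Section 8.1.2.1.4 also recognises delayed anaphylaxis or allergic reactions, which a 30-minute check can miss.

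Spacing the sentinels is useful for safety mainly if something is learned about one before the next is dosed. Neither sentinel passage asks anyone to contact the previous sentinel during the interval. The 7-day condition in the synopsis protects participants enrolled afterwards. It does not protect sentinels two to five, for whom the interval is the only stated safeguard particular to the sentinel group.

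**Working it through.** **Inputs.** Visit 2 at Week 1 ± 2 days (Table S2; SAP 8.3, Table 2: day 7 ± 2). Observation of 30 minutes (Section 7.1.1). Five sentinels at least 24 hours apart (synopsis; Section 3). Dose 2 at Week 8 and telephone visit at Week 9 ± 3 days (Table S2).

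**1. Visit 2 window.** 7 − 2 = 5 and 7 + 2 = 9, which reproduces the SAP's day 5 to 9.

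**2. Gap after dose 1.** Table S2 has no column between Visit 1 and Visit 2. A local reaction that begins on the evening of day 0 and is held as 7.4 directs reaches the site about 5 to 9 days later. The 24 hours in 8.3.1 start only then.

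**3. Sentinel timeline at the minimum spacing.**

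| Sentinel | Dosed (day) | Earliest Visit 2 | Latest Visit 2 |
|---|---|---|---|
| 1 | 0 | 5 | 9 |
| 2 | 1 | 6 | 10 |
| 3 | 2 | 7 | 11 |
| 4 | 3 | 8 | 12 |
| 5 | 4 | 9 | 13 |

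All five doses (days 0 to 4) come before day 5, the earliest scheduled follow-up or diary review of any sentinel. Scheduled observation covers 0.5 of each 24 hours: 0.5 / 24 = 2.1%.

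**4. Seven-day gate in the synopsis.** The last sentinel completes 7 days on day 4 + 7 = 11, with Visit 2 between day 9 and day 13. Visit 2 and the diary can therefore largely inform this gate. A permitted Visit 2 on a participant's own day 5 or 6, however, falls before the 7 days are complete.

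**5. After dose 2.** With dose 2 on day 56, the telephone visit falls on day 63 ± 3, that is 63 − 3 − 56 = 4 to 63 + 3 − 56 = 10 days later. Table S3 (dose at Week 12, call at Week 13) and Table S4 (Weeks 8 and 9) give the same 4 to 10 days. The 5 to 9 days in step 2 apply to dose 1 only.

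**6. Overlap of 7.4 with other rules.**
- With 8.3.1 it is direct: a Grade 3 local symptom falls under both.
- With 8.3.2 it is small: the triggers are related life-threatening or Grade 4 events, related deaths, related serious events, and related anaphylaxis of Grade 3 or greater. A local sign counts only at the extreme.

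**The case against.** A reader might infer that the sentinel interval and the immediate halt have no data at all to act on. The documents do not support that. The 30-minute check looks for anaphylaxis, and related Grade 3 or greater anaphylaxis is itself a halt trigger. Unscheduled visits with adverse-event review exist (Sections 7.1.11 and 7.2.11), and Table S2 marks injection-site examination in the unscheduled column. Serious events go to the sponsor when they become known (Section 8.1.7) and immediately to the ethics committee and the sponsor (Section 15.2). Section 7.4 concerns local signs and does not forbid an earlier call.

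Four further points carry weight.
- Section 8.3.1 governs site-to-sponsor timing, so it and 7.4 do not formally contradict each other.
- Neither sentinel passage calls the 24 hours a data-review step, and the exposure concerned is limited to five people.
- The diary (Appendix B) and the consent and contact pages are not in the supplied text, and between-visit contact instructions would normally sit there.
- The SAP (Section 4.1) reports the Phase IIa Visit 4 interim in the past tense, so sentinel dosing was over when it was written.

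These points narrow the concern but do not remove it. The unscheduled-visit sections list procedures without saying when a participant should call. The serious-event rules depend on the site already knowing. If the diary or consent form does ask for prompt calls, 7.4 says something different and still needs correcting.

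**Conclusion.** The concern holds in a limited form. Section 7.4, followed as written, can delay site knowledge of a Grade 3 local reaction after dose 1 until day 5 to 9, although the protocol treats that reaction as expedited. At the minimum spacing, all five sentinels can be dosed before any has a scheduled contact beyond the 30-minute check. The two sentinel gates also differ and must be reconciled.

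This assumes that the participant follows 7.4 literally, that spacing is at the permitted minimum, and that the unseen pages contain no overriding instruction. The documents give no rate for reactions that begin between 30 minutes and the next contact, so no probability of a missed event can be stated. The effect on the halting rule is minor. This is a correction worth making because it is cheap; it does not show that safety monitoring is absent.

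**What to change.** 1. Reconcile Section 7.4 and the diary instructions with Section 8.3.1, so that waiting for the next visit does not apply to events the protocol already classes as expedited (Grade 3 or greater symptoms, allergic reactions). Participants should report those to the site promptly. First check what Appendix B and the consent form say.
2. Reconcile the sentinel text in the synopsis and Section 3 with the adverse-event collection schedule, so that the sponsor's own 24-hour interval includes a documented adverse-event contact, for example a telephone call.
3. Reconcile the two sentinel gates, including the period and the double negative in Section 3.

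The choice of clinical criteria stays with the sponsor. The cost is up to five short calls and a few changed sentences in 7.4, the diary and the sentinel text, with perhaps some extra unscheduled calls. No visits or participants are added. Where dosing is already complete, the study report can state which between-visit contacts took place.

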7.5 Immunogenicity assessments

Blood to obtain serum and PBMCs for immunogenicity assessments will be collected at all visits, except for Visit 2 and unscheduled visits. Serum will be evaluated for antibody responses by ELISA against the SARS-CoV-2 S and ORF3a proteins. Serum will also be evaluated for neutralizing antibody responses. Induction of T cells will be determined by ELISPOT to determine interferon gamma (IFN- γ) responses of PBMCs against pools of 15-mer peptides spanning each target antigen.

8 Safety assessments

8.1.1 Safety Parameters

- 1) Adverse events
- 2) Vital signs
- 3) Laboratory evaluations
- 4) Injection site reaction evaluations

8.1.2 Safety Evaluations

8.1.2.1 Adverse Events (AEs)

8.2.1.1 Definition of Adverse Events

An AE (also referred to as an adverse experience) is defined as any unfavorable and unintended sign, symptom or laboratory abnormality that is temporarily associated with the use of a drug or treatment and does not imply any judgement about causality. An adverse event can arise with any use of a drug or treatment regardless of route of administration, dose, and may be delayed after a drug or treatment has been discontinued. An adverse event is not the same as an “overdose”; an overdose is a dose-related event specifically caused by exposure to an increased amount of drug.

Adverse drug reactions (ADRs) are all adverse and unintended reactions that occur at any dose of a study drug, and the causal relationship with the study drug cannot be denied.

Adverse events of Special Interest (AESI) include enhanced disease of the immune system, and the following symptoms can be monitored more closely:

- Patient with documented vital signs with: respiratory rate of ≥ 30 breaths per minute, heart rate ≥ 125 per minute, SpO₂ of $\leq 93\%$ on room air, or PaO₂/FiO₂ of < 300 mm Hg.
- Respiratory failure (requirement for high-flow oxygen, non-invasive ventilation, mechanical ventilation, or ECMO)
- Shock (systolic BP of < 90 mm Hg, or diastolic BP < 60 mm Hg, or need for vasopressors)
- Significant acute renal failure, hepatic or neurologic dysfunction
- Admission to ICU
- Death

An unexpected AE is:

- Not identified in the IB or otherwise not expected from the characteristics of the clinical material
- Not listed at the specificity or severity that has been previously observed

Treatment emergent AEs (TEAE) include the following:

- Post-treatment complications that occur as a result of protocol mandated procedure
- Any pre-existing condition that increases in severity, or changes in nature during or as a consequence of the study drug, will also be considered an AE
- Complications and termination of pregnancy; see Section 7.1.8 for additional information.
-

Study related AEs do not include the following:

- Elective medical or surgical procedures
- Non-elective medical or surgical procedures (Medical or surgical procedure (e.g. surgery, endoscopy, extraction, blood transfusion); On the other hand, the conditions that led to these procedures are considered adverse events.
- Pre-existing diseases or conditions or laboratory abnormalities present or detected before study enrollment or prior to the first administration of study drug and dose not worsen
- Conditions where no undesirable medical event has occurred (e.g. hospitalization for planned surgery, hospitalization for social and/or accommodation)
- Incorrect or increased dose administration of study drug without adverse clinical sequelae
- Pre-existing diseases or conditions or laboratory abnormalities present or detected before study enrollment or prior to the first administration of study drug and dose not worsen. It is considered pre-existing and is recorded as a medical history in the eCRF.
- Any laboratory abnormality that is considered as non-significant
- Uncomplicated pregnancy
- An induced termination of pregnancy without medical reason

8.1.2.1.2 Serious Adverse Events (SAEs)

A SAE is any AE that meets one of the following conditions

- Death
- Life-threatening event.
- Event that requires inpatient admission to a hospital; (If hospitalization or extension of the existing hospital stay is required during the observation period defined in the clinical trial protocol (even if the hospitalization is made as a preventive measure for continuous observation, one night at the hospital regardless of the length of stay) This includes the case of doing things).

Note: Observation, non-hospital evaluation, in a physician's office, hospital, or other emergency care setting, regardless of the duration of observation, is not a SAE;)

- Results in congenital anomaly or birth defect;
- Results in persistent or significant disability/incapacity;

Is an important medical event that may not result in death or be life threatening, but based upon appropriate medical judgment, may jeopardize the participant and may require medical or

surgical intervention to prevent one of the outcomes listed above. Examples of such medical events include allergic bronchospasm and newly occurred convulsions.

8.1.2.1.3 Solicited local/systemic AE

In the vaccination of this investigational drug, a feeling of pulling the skin may occur due to suction, and potential adverse events of the investigational drug may include erythema, pain, heat, or partial swelling at the injection site. Other adverse events that occur are included in the unexpected adverse events.

The solicited local and systemic adverse events can be summarized as follows.

Table 8.1.2.1.3-1 Solicited local/systemic AE

Common	
 Mild to moderate administration site pain, erythema, tenderness, swelling, induration Malaise/fatigue, myalgia, or headache in the first few days following injection Visible lesion(s) at the injection site, such as erythematous papules with eschar, hypopigmentation, hyperpigmentation
Less common	
 Administration site bruising/ecchymosis, hematoma or pruritus Arthralgia or nausea Injection site hematoma, bruising/ecchymosis, laceration, other transient lesions, or bleeding related to the injection procedure Eosinophilia
Uncommon or rare	
 Administration site, laceration, other transient lesions, or bleeding related to the injection procedure Severe administration site pain or tenderness Rash following injection/EP Keloid scar or hypertrophic scar formation Transient changes in clinical laboratory values
Unknown frequency or theoretical potential risks	
 Severe localized administration site reaction, such as sterile abscess or secondary bacterial infection Allergic reaction, including urticaria, angioedema, bronchospasm, or anaphylaxis Chills, flu-like syndrome Muscle damage at the administration site Autoimmune disease Effects on the fetus and on pregnancy

